**Official Title: Intelligent and Adaptive Control Applied to Powered Walkers**

**NCT05465239**

**STUDY PROTOCOL**

**Brief Summary/Abstract**

Barron Associates, Inc. (BAI) has teamed with the University of Virginia's (UVA's) Motion Analysis and Motor Performance (MAMP) laboratory to propose development of an advanced control and computer learning strategy that will intelligently drive a powered walker for people with walking disabilities. The aim of the control strategy is to provide powered assistance that optimally reduces the metabolic cost of walking. The goal of the proposed intelligent walker is to reduce the workload of walking, keeping this population walking longer, providing critical exercise, continued muscle development and improved quality of life.

## Background

### 1. Provide the scientific background, rationale and relevance of this project.

Many individuals with walking disorders due to neuromuscular disabilities, such as cerebral palsy (CP), use walkers or crutches to aid their mobility unless impairment is so severe as to require the use of a wheel chair. United Cerebral Palsy (UCP) reports that an estimated 764,000 individuals in the United States have one or more symptoms of CP, and a recent multisite UCP study of school-age children found that 24.8% of these individuals use walkers [1] and it is estimated that more than 10,000 pediatric walkers are sold each year in the U.S. Walkers are often equipped with four wheels of varying diameters, which can be mounted on fixed axles or can swivel on casters. Anterior walkers are configured to have the main cross frame in front of the user, whereas posterior walkers position this frame behind the user. Yet both configurations generally “surround” the user with supporting frames. Fig. 1 shows some typical, commercially available anterior and posterior unpowered walkers. Walking requires mechanical work to lift/lower and accelerate/decelerate the center of mass (CoM) of the body. The energy recovered as a result of exchange between potential energy (PE) and kinetic energy (KE) is the main energy saving mechanism of walking, minimizing metabolic expenditure in healthy individuals [2]. However, in individuals with walking disabilities, valuable energy is lost at each gait cycle due to the misappropriation of KE and PE during movement of the CoM. The net result is that energy recovery is substantially reduced and walking becomes a high workload activity – even with typical walkers or crutches. In children with CP, the metabolic cost of walking can be up to *ten* times that of children with typical development, due to poor energy recovery when walking [3-5]. Bennett et al. [6] found mechanical work performed by children with CP to be more than double that of children with typical development, in part due to the fact that children with CP were only able to recover 44% of the available energy, in contrast to 66% recovered by unimpaired children. Individuals with CP or other disabilities can have compromised motor control, impaired balance, and weakness, all of which can make ambulating difficult – even with a walker. Studies of walker use by children with CP have focused on the kinetics, kinematics, and tradeoffs regarding walker configurations [7-12]. This research has shown that the use of current walkers does not alter the relatively large effort required for these children to walk; as a result, fatigue itself may limit their participation in activities. The walker is fundamentally used for balance, or “something to hold on to” while walking, not to reduce the workload of walking. Exacerbating the problem is the fact that most of these walkers are designed to be large and heavy to meet the requirements for stability/balance. Further, some walker configurations have no wheels or have fixed wheels that do not turn. Thus, the walker has to be dragged or picked up during turning, which is an essential part of moving during everyday activities [13]. These difficulties with walking and the use of cumbersome walker designs often result in this population eventually using wheelchairs, which reduces their mobility and ability to fully

**Fig. 1. Typical Unpowered Walkers**

participate in many social settings. Studies have reported up to 79% of children with CP to be ambulatory at six years of age, (the rest already requiring wheelchairs). However, among adults with CP, 63% reported owning and using one or more wheelchairs and only 21% reported never using a wheelchair. The majority (59%) reported decreased walking ability before reaching 34 years of age; by age 44 the percentage was 90%. [14]

It is important to keep individuals with these types of walking disabilities ambulatory for as long as possible. The significance of this effort is to provide a walker that reduces the workload of walking, keeping this population walking longer, providing critical exercise and continued muscle development. This will help the individual stay active longer, and perhaps prevent the use of a wheelchair. This will greatly improve their quality of life, gaining key physiological, mental, and social benefits.

### **Hypothesis to be Tested**

Hypothesis: A powered posterior walker will have a significant effect on A) the mobility and B) the efficiency of the gait patterns for typically developed individuals and those of children with cerebral palsy

1. Hypothesis: An adaptive learning control algorithm can be implemented for a powered walker to develop optimal movement and efficiency in the gait patterns of typically developed individuals and those of children with cerebral palsy

### **Study Design: Biomedical**

1. **Will controls be used?** Yes

► **IF YES, explain the kind of controls to be used.**

Matching gait analysis will be conducted on typically developed individuals with and without the walker

2. **What is the study design?**

This study design is a repeated measures crossover study. Repeated measures ANOVA will be performed to determine any global effects of the powered walker on the efficiency Kinematics, and force loads applied during walking.

3. **Does the study involve a placebo?** No

4.

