**3. List any restrictions on use of other drugs or treatments. None**

## Statistical Considerations

### 1. Is stratification/randomization involved? No

### 2. What are the statistical considerations for the protocol?

BAI and UVA will work together to prepare the trial results for statistical analysis. The analysis shall include testing for within-subject differences of oxygen consumption, walking speed, and device acceptance scores based on participant's use of the baseline (unpowered) and powered walkers. Past experience by the BAI/UVA team gives us the qualifications to complete statistical analyses in-house. Success will be defined by the controlled/powered walker significantly reducing oxygen consumption, increasing walking speed, and having superior device acceptance compared to the unpowered walker.

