### 3. Provide a justification for the sample size used in this protocol.

**Table 1. Detectable Differences in Powered Minus Unpowered Walker Outcomes.**

Outcome Measure	Standard Deviation of Paired Differences	Paired Data Correlation	Detectable Difference ( $\Delta$ )	Detectable Effect Size
Oxygen Consumption	4.61 mL/kg/min	0.256	-3.0 mL/kg/min	0.65
Walking Speed	4.16 m/min	0.963	3.5 m/min	0.85
Device Acceptance	2.26 units	-0.019	1.3 units	0.58

Power analysis: Assuming a significance level of  $\alpha=0.05$ , based on the standard deviations of paired differences listed in column 2 of Table 1 and the empirical measurement correlations in column 3 of Table 1, a one-sided paired t-test achieve 80% power to detect a mean of the paired differences listed in column 4 of Table 1. These represent medium-to-large effect sizes (column 5 of Table 1), but magnitudes that we would expect to achieve under the alternative hypothesis.

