### 4. What is your plan for primary variable analysis?

Include a sketch of the analysis to assess primary study objectives.

Each patient will provide one trial of unpowered walker data and two trials of powered walker data. Thus, a total of two *difference* combinations (*i.e.*, *powered minus unpowered outcomes*) for each of 10 patients will yield 20 difference ( $\Delta$ ) values for *each* outcome measure:  $\Delta_{\text{oxygen}}$  consumption,  $\Delta_{\text{walking speed}}$ , and  $\Delta_{\text{device acceptance}}$ . To assess the unpowered to powered walker changes in outcomes based on each set of 20 pooled  $\Delta$  values, a one-sided paired t-test will be used to test the following null hypothesis:  $H_0: \Delta_{\text{oxygen consumption}} = 0$  versus the alternative hypothesis  $H_a: \Delta_{\text{oxygen consumption}} < 0$ ;  $H_0: \Delta_{\text{walking speed}} = 0$  versus the alternative hypothesis  $H_a: \Delta_{\text{walking speed}} > 0$ ; and  $H_0: \Delta_{\text{device acceptance}} = 0$  versus the alternative hypothesis  $H_a: \Delta_{\text{device acceptance}} > 0$ .

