### 5. What is your plan for secondary variable analysis? NA

### 6. Have you been working with a statistician in designing this protocol? No

### 7. Will data from multiple sites be combined during analysis? No

**Barron Associates, Inc.**  
**September 1, 2023**

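### The repeated measures ANOVA in the design section is not reconciled with the one-sided t-tests that decide success, and kinematics and force loads are tested without belonging to any tier of the analysis

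*Combined protocol and SAP*

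**What the plan says.** Study Design: Biomedical, item 2, calls the trial a repeated measures crossover and states: "Repeated measures ANOVA will be performed to determine any global effects of the powered walker". The outcomes it lists for this analysis are efficiency, kinematics and force loads. It gives no factors, levels, variables, significance level or number of tests.

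Statistical Considerations describes a different analysis. Item 2 plans "testing for within-subject differences of oxygen consumption, walking speed, and device acceptance scores" and defines success as the powered walker "significantly reducing oxygen consumption, increasing walking speed, and having superior device acceptance compared to the unpowered walker". Item 3 bases the sample size on the same kind of test: "a one-sided paired t-test achieve 80% power to detect a mean of the paired differences". Item 4 gives the primary analysis: "a one-sided paired t-test will be used to test the following null hypothesis", with a directional alternative for each of the three outcomes. Item 5 reads "What is your plan for secondary variable analysis? NA". None of these items mentions an ANOVA, kinematics or force loads.

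The Hypothesis to be Tested section states that "A powered posterior walker will have a significant effect on A) the mobility and B) the efficiency of the gait patterns". This is meant to hold both in the control group and in children with cerebral palsy. The section names no variable for mobility or efficiency and does not refer to the success definition.

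**The concern.** Two analyses are promised and nothing says how they relate. Three gaps follow.

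- If efficiency is measured by oxygen consumption, one set of data has two tests, one directional and one not. They can disagree, and the plan does not say which one counts.
- Kinematics and force loads are to be tested but are neither primary nor secondary, so nothing governs their number, error rate or interpretation.
- The hypothesis asks for a significant effect on mobility and efficiency without linking them to the three success outcomes. If the success definition failed, a significant gait variable could still be put forward as support for one part of the hypothesis.

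At stake is what the final report may claim beyond the declaration of success.

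**Working it through.** **1. The plan's own figure.** Item 3 states 80% power for a one-sided paired t-test at alpha 0.05, with no n beside it. Item 4 gives 20 differences from 10 patients. The documents do not state an effective sample size. If it is taken as 20/(1 + r), with r the correlation in Table 1, noncentral-t power with d = difference/SD recovers all three rows:

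| Outcome | d | 20/(1 + r) | One-sided power |
|---|---|---|---|
| Oxygen consumption | 3.0/4.61 = 0.651 | 20/1.256 = 15.92 | 79.7% |
| Walking speed | 3.5/4.16 = 0.841 | 20/1.963 = 10.19 | 79.8% |
| Device acceptance | 1.3/2.26 = 0.575 | 20/0.981 = 20.39 | 80.5% |

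The power statement therefore belongs wholly to the one-sided t-tests. No power or alpha is given for the ANOVA.

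**2. Two tests on one outcome, no true effect.** Assume that efficiency is oxygen consumption, that each subject contributes one mean difference, and that the ANOVA has two levels, so that F is the square of the same t. The one-sided test rejects in the lower 5%. The F-test rejects in the lower 2.5%, already included, and the upper 2.5%. Accepting either gives 5% + 2.5% = 7.5%. Simulation (10 subjects, 100,000 runs per correlation) gave 7.3% to 7.6%. With a three-level ANOVA (one unpowered and two powered trials) it gave 8.4% to 8.7%.

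**3. The same two tests at the planned oxygen effect.** Under the same assumptions:

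| n | One-sided power | Two-sided power | Gap in points (unrounded figures) |
|---|---|---|---|
| 10 | 60.1% | 45.1% | 14.9 |
| 15.92 | 79.7% | 68.0% | 11.7 |
| 20 | 87.7% | 78.8% | 8.9 |
| 24 | 92.6% | 86.3% | 6.3 |

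The gap is the share of trials in which the t-test is significant and the F-test is not.

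**4. Gait variables.** For k independent tests at 0.05, the chance of at least one false positive is 1 - 0.95^k:

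- k = 3 (one overall test for each of the three domains named): 1 - 0.857 = 14.3%
- k = 5: 1 - 0.774 = 22.6%

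The plan does not state k. Positive correlation between the variables lowers these figures.

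**5. The success definition.** All three outcomes must be significant. If each component test is valid at 5%, false success is at most 5%, whatever the ANOVA shows.

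**The case against.** The strongest reply is that the plan already has a decision rule. Success needs oxygen consumption, walking speed and acceptance together, so no kinematic or force result can produce it. That stands. A reader might infer that the hypothesis can be claimed from any one of an unlimited set of tests. The documents do not support this: the success definition excludes it, and the hypothesis names both mobility and efficiency, so one gait variable would at most be offered for one part.

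A second reply is that the two analyses need not contradict each other. Efficiency is never defined. The Brief Summary aims to reduce the metabolic cost of walking, which points to oxygen consumption. The Background also discusses mechanical energy recovery, which would make efficiency a gait-laboratory quantity. The punctuation of the ANOVA sentence leaves its variable list uncertain too. This also stands: the analyses are unreconciled, not shown to conflict. The gap remains on the other reading, because efficiency would then have no test in the primary plan and only an unspecified ANOVA.

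A third reply is that the F-test may not be the two-sided form of the t-test, since the factors are not given and there are three trials per patient and a control group. That is correct, and it makes the figures in steps 2 and 3 conditional.

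**Conclusion.** The point holds as a gap in specification. The plan names two analyses without relating them, and it tests kinematics and force loads outside any tier. It does not undermine the success definition.

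The size is moderate and conditional. One outcome tested both ways carries 7.5% false positives instead of 5%, if efficiency is oxygen consumption and the F-test has two levels. The chance of at least one false gait finding is 14% to 23% for three to five independent tests, with k assumed. Much higher rates follow from assuming ten or twenty variables, but the documents give no basis for such a count, and none of these rates applies to the success rule.

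A separate matter affects the remedy. The primary test pools two differences per patient as if independent; in simulation with 10 patients its type I error was about 9%. It should not be made the sole deciding test in that form.

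**What to change.** 1. State that efficiency is judged by oxygen consumption and mobility by walking speed. Each gets one pre-named within-subject test of powered minus unpowered, using one mean difference per subject. The success definition in Statistical Considerations, item 2, decides success. Remove efficiency from the ANOVA sentence in the design section, or state that the ANOVA is supportive only.
2. Replace the answer to item 5 with: kinematics and force loads are secondary. They are reported as within-subject powered-minus-unpowered estimates with 95% confidence intervals, or with Holm-adjusted tests over a listed set of variables. On their own they cannot support success or the study hypothesis.
3. State that the same contrast is estimated in the typically developed group. The primary plan refers only to 10 patients and names no test for that group, so this part of the hypothesis needs its own analysis. The design section describes controls walking with and without the walker; confirm that both powered and unpowered data exist for them.

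The cost is a few sentences. Gait findings lose confirmatory status. The timeline entry describes recruitment in the past tense, so if any data have been examined the change must be dated and declared as made afterwards.

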### Human Participants

**Ages:** 5-30

**Sex:** Male and female

**Race:** Any

**Subjects- see below**

**1. Provide target # of subjects (at all sites) needed to complete protocol.**

48 subjects total, 24 individuals with CP and 24 typically developed subjects.

**2. Describe expected rate of screen failure/ dropouts/withdrawals from all sites. 2**

**3. How many subjects will be enrolled at all sites? 50**

**4. How many subjects will sign a consent form under this UVa protocol? 50**

**5. Provide an estimated time line for the study.**

48 subjects were recruited in year 2.

### Inclusion/Exclusion Criteria

**1. List the criteria for inclusion**

Typically developed subjects; No walking disabilities

Subjects with CP; Diagnosed with spastic CP  
GMFCS level II-III  
Ages 5-25 inclusive  
No surgeries in last 6 months  
Able to ambulate 40ft unaided (excluding walker)  
Understand and follow commands

**2. List the criteria for exclusion**

Typically developed subjects; Observed intramuscular pathology

Subjects with CP; Mental retardation  
Severe uncontrolled seizures  
Leg or foot surgery in last 12 months  
Surgery or significant injury in last 6 months affecting walking ability  
Inability to ambulate unassisted (other than walker) 40ft without stopping to rest  
Inability to understand or follow commands

**3. List any restrictions on use of other drugs or treatments. None**

## Statistical Considerations

### 1. Is stratification/randomization involved? No

### 2. What are the statistical considerations for the protocol?

BAI and UVA will work together to prepare the trial results for statistical analysis. The analysis shall include testing for within-subject differences of oxygen consumption, walking speed, and device acceptance scores based on participant's use of the baseline (unpowered) and powered walkers. Past experience by the BAI/UVA team gives us the qualifications to complete statistical analyses in-house. Success will be defined by the controlled/powered walker significantly reducing oxygen consumption, increasing walking speed, and having superior device acceptance compared to the unpowered walker.

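### The crossover does not state or control the order of the unpowered and powered trials, so order effects can enter the difference that decides all three outcomes

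*Combined protocol and SAP*

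**What the plan says.** Study Design, item 2: "This study design is a repeated measures crossover study". Statistical Considerations, item 1: "Is stratification/randomization involved? No".

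The primary analysis (Statistical Considerations, item 4) sets out the data: "Each patient will provide one trial of unpowered walker data and two trials of powered walker data". The outcomes are tested as powered minus unpowered, each with a one-sided paired t-test. Neither that test nor the repeated measures ANOVA named under Study Design carries a period, sequence or position term. No section describes counterbalancing, rest or washout.

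Success (Statistical Considerations, item 2) means the powered walker "significantly reducing oxygen consumption, increasing walking speed, and having superior device acceptance compared to the unpowered walker". All three parts rest on the same contrast. The nearest thing to an order is the phrase "use of the baseline (unpowered) and powered walkers" in that item, where the word baseline may mean the first trial or only the comparator.

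**The concern.** Pairing removes stable differences between subjects. It does not remove the effect of when in the sequence a trial is done. If every patient follows the same order, trial position and walker are fully confounded and no analysis can separate them. Repeating the powered trial does not help, because both differences share the single unpowered trial and so share its position.

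An order effect is plausible here. The Background says of children with cerebral palsy that "fatigue itself may limit their participation in activities", and a new device invites practice and familiarisation. At stake is the reading of the result in either direction: a significant difference could be partly order, and a null one could hide a real benefit.

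**Working it through.** **Inputs.** From Table 1 (Statistical Considerations, item 3), SD of paired differences and detectable difference: oxygen 4.61 and 3.0 mL/kg/min (in absolute value); speed 4.16 and 3.5 m/min; acceptance 2.26 and 1.3 units. One-sided alpha is 0.05. The primary analysis names 10 patients and 20 differences. The size of any order effect is not in the documents; 10%, 25% and 50% of the Table 1 difference are assumptions.

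**The plan's own figures.** Effect sizes: 3.0/4.61 = 0.651, 3.5/4.16 = 0.841, 1.3/2.26 = 0.575 (stated 0.65, 0.85, 0.58). Power of the one-sided paired t-test is P(T > t crit), with T noncentral t on n − 1 df and noncentrality d√n. At n = 20 it is 87.7%, 97.6% and 79.8%; at n = 10 it is 60.1%, 79.1% and 51.4%. The stated 80% is not met for all three at either n. That is a separate matter and the point here does not depend on it.

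**How order enters.** Suppose outcomes drift by c per trial position. The mean of the two powered trials minus the unpowered trial is then shifted as follows:
- unpowered first: (2 + 3)/2 − 1 = +1.5, so +1.5c
- unpowered in the middle: (1 + 3)/2 − 2 = 0
- unpowered last: (1 + 2)/2 − 3 = −1.5, so −1.5c

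For any additive position effects p1, p2, p3, the three shifts sum to zero, so giving the three sequences equal weight removes them.

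**Illustration.** Assume a fixed order that favours the powered walker, no true effect, and one difference from each of 10 patients with the Table 1 SD. The 20 pooled differences are not used: two differences that share one unpowered trial are not independent. Treating them as independent already gives an error of about 9% to 11% with no order effect, at within-patient correlation 0.5 to 0.75.

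With n = 10, t crit is 1.833 on 9 df. For oxygen at 25%: shift 0.25 × 3.0 = 0.75; 0.75/4.61 = 0.163; noncentrality 0.163 × √10 = 0.514; rejection probability 12.1%.

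| Order effect, % of Table 1 difference | Oxygen | Speed | Acceptance |
|---|---|---|---|
| 0 | 5% | 5% | 5% |
| 10 | 7% | 8% | 7% |
| 25 (0.75, 0.875, 0.325 in outcome units) | 12% | 15% | 11% |
| 50 | 24% | 34% | 21% |

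**All-three rule.** Joint false success cannot exceed the smallest entry in a row. By simulation (trivariate normal differences, n = 10):

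| Order effect | Correlation 0 | 0.5 | 0.8 |
|---|---|---|---|
| 0 | 0.01% | 0.4% | 1.5% |
| 25% | 0.2% | 2% | 5% |
| 50% | 2% | 7% | 13% |

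**Opposite direction.** If the true effect equals the Table 1 difference and a 25% order effect works against it, the same formula with 0.75 × d at n = 10 gives power of 41%, 58% and 35%, against 60%, 79% and 51% without it.

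**The case against.** The strongest reply is that the declared success claim is less exposed than single-outcome error rates suggest. It needs all three outcomes. At a 25% order effect, joint false success stays below 5% unless the outcomes are correlated at about 0.8, and even then the order effect must favour the powered walker on every outcome. This stands. The per-outcome figures show how the individual tests behave, not the risk to the joint claim.

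Other replies also carry weight:

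- The randomisation item is a combined form question and may concern group allocation. The text available for review has no procedures section, and Study Design item 4 is blank. A reader might infer that counterbalancing was ruled out; the documents do not say so.
- A reader might infer a fixed unpowered-first order that flatters the powered walker. The word baseline is compatible with that order but does not establish it. Even in that order, practice would favour the powered walker and fatigue would count against it.
- The fatigue statement concerns taking part in activities, not successive trials in one session, and concerns children with cerebral palsy, not the controls. It supports plausibility only.
- Randomised order has its own risk, carryover from powered to unpowered trials, which unpowered-first avoids. Neither bias can be sized from the documents.
- Recruitment appears complete: "48 subjects were recruited in year 2". Randomising may no longer be possible.

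None of these removes the gap. As written, nothing in the design or analysis keeps trial position out of the contrast, and a reader cannot tell how much of a result reflects it.

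**Conclusion.** The point holds as a design weakness that should be fixed. The plan leaves trial position uncontrolled in the one contrast that decides all three outcomes. Bias is possible, not shown, and its direction is unknown; the documents do not support saying that the results are biased or that they favour the powered walker.

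An assumed order effect of 10% to 50% of the Table 1 difference would raise one-sided error to 7% to 34% per outcome in 10 patients. Joint false success passes 5% only with a large order effect or strongly correlated outcomes. These figures assume a fixed order, an effect in the same favourable direction on all three outcomes, 10 patients and the Table 1 SDs for one difference per patient. The documents also give 24 subjects with cerebral palsy and 24 controls, and state the three-trial scheme only for patients.

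**What to change.** **If data remain to be collected.** For every subject who does the three-trial scheme, randomise or counterbalance whether the unpowered trial comes first, in the middle or last. Analyse one difference per patient: the mean of the two powered trials minus the unpowered trial. Weight the three sequences equally; where their sizes differ, average the three sequence means with the pooled within-sequence SD on n − 3 df. If a trial-level model with a position term is used instead, include a subject-by-condition random effect. Without one, simulated error at n = 24 with no order effect was 8.2% when half the paired-difference variance was subject-specific.

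State two assumptions that this design does not remove: no carryover from a powered trial to a later unpowered one, and no learning specific to the powered walker. The second matters because the hypothesis is that "An adaptive learning control algorithm can be implemented for a powered walker", so a change between the two powered trials may be part of the device effect.

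**If data are already collected.** Report the order each subject followed. Adjust for position if it varied. If it was fixed, say that the estimate includes any order effect and do not attribute the whole difference to the powered walker. If order was in fact counterbalanced, say so and describe how.

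**Cost.** A randomisation list and up to 2 df; the scheme adds no trials, though the documents give no visit schedule to check against. With half the paired-difference variance assumed subject-specific, power (oxygen, speed, acceptance) at 8/8/8 per sequence is 95.1%, 99.6% and 89.8%, against 95.2%, 99.6% and 89.9% for the plain patient-level t-test. At 4/3/3 it is 62.5%, 81.3% and 53.7%, against 65.0%, 83.6% and 56.0%. Two thirds of subjects would use the powered walker before the unpowered trial, so a carryover that improves the unpowered trial by 25% of the true effect would understate that effect by 25% × 2/3 = 17%. With recruitment finished, the cost is reporting the order and perhaps one re-analysis.

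### The 80% power is per test, but success requires all three outcomes; from Table 1, joint power is about 68% with 20 independent differences and 24–63% with 10 patients (independent outcomes)

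*Combined protocol and SAP*

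**What the plan says.** All references are to the combined protocol and SAP.

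- **Statistical Considerations, item 2** defines success as the powered walker "significantly reducing oxygen consumption, increasing walking speed, and having superior device acceptance compared to the unpowered walker". The three results are joined by a conjunction. No outcome is singled out as decisive, and secondary analysis is marked as not applicable (item 5).
- **Item 3 (sample size)** states, at a significance level of 0.05, that "a one-sided paired t-test achieve 80% power to detect a mean of the paired differences listed in column 4 of Table 1". Each row of Table 1 is one outcome. The section gives no number of subjects and no power for the three outcomes together.
- **Item 4 (primary analysis)** takes one unpowered and two powered trials per patient. The two differences "for each of 10 patients will yield 20 difference" values per outcome, and for each outcome "a one-sided paired t-test will be used to test the following null hypothesis".
- **Subjects, item 1** gives a different number: "48 subjects total, 24 individuals with CP and 24 typically developed subjects".

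**The concern.** The only power figure in the plan concerns one test at a time, while the verdict on the walker depends on three tests all succeeding. Joint power can never exceed that of the weakest test, and is lower unless the three results move together almost perfectly. Item 3 describes the Table 1 differences as ones the team would expect to achieve. If the walker did achieve all of them, the trial could still miss its own definition of success more often than the one-in-five risk that 80% suggests. The sample size has not been justified for the decision it is meant to support.

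**Working it through.** **Inputs (Table 1).** Mean difference divided by SD of paired differences:
- oxygen consumption: 3.0/4.61 = 0.651
- walking speed: 3.5/4.16 = 0.841
- device acceptance: 1.3/2.26 = 0.575

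The test is a one-sided paired t-test at 0.05.

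**Formula.** Power = P(T > t(0.95, n−1)), where T is noncentral t with n−1 degrees of freedom and noncentrality d√n. If outcomes are independent, joint power is the product of the three powers. Whatever the dependence, it lies between (sum of the three − 2), or 0 if that is negative, and the smallest of the three.

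**Step 1: reproduce the stated 80%.** Oxygen reaches it at n = 16 (79.9%), speed at about n = 10 (79.1%) and acceptance at n = 20 (79.8%). No single n gives 80% on all three rows. At n = 20, the plan's count of values, only the acceptance row reproduces.

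**Step 2: joint power with 20 independent differences.** The powers are 0.877, 0.976 and 0.798.
- Independent outcomes: 0.877 × 0.976 × 0.798 = 0.683.
- Lower bound: 0.877 + 0.976 + 0.798 − 2 = 0.651. Upper bound: 0.798.

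**Step 3: allow for 10 patients.** Each patient's two differences subtract the same unpowered trial, so they are not independent. Take one averaged difference per patient and treat the Table 1 SD as that of a single difference. The SD of the average is then SD × √((1+ρ)/2), where ρ is the within-patient correlation of the two differences. The documents give no ρ, so a range is shown (n = 10):

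| Assumed ρ | Oxygen | Speed | Acceptance | Joint, independent outcomes | Joint, at most |
|---|---|---|---|---|---|
| 0 | 85% | 97% | 77% | 63% | 77% |
| 0.5 | 71% | 88% | 62% | 38% | 62% |
| 1 | 60% | 79% | 51% | 24% | 51% |

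Even the most favourable cell is below 80%.

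**Step 4: the 24 CP subjects already planned,** one averaged difference each:

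| Assumed ρ | Oxygen | Speed | Acceptance | Joint, independent outcomes |
|---|---|---|---|---|
| 0 | 99.7% | 100% | 99% | 98% |
| 0.5 | 97% | 99.9% | 93% | 91% |
| 1 | 93% | 99% | 86% | 79% |

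At ρ = 1 the bounds over any dependence between outcomes are 78% and 86%.

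The correlations printed in Table 1 do not fill the gap. They appear to relate powered to unpowered values within one outcome, not one outcome to another or one powered trial to the next.

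**The case against.** Four arguments can be made for the plan.

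1. **It claims no joint power.** Item 3 says that a t-test reaches 80%, which is a per-test statement, so no joint figure has been miscalculated. This stands: the fault is an omission. But the 80% is the only sample-size justification offered, and it concerns a different event from the success rule.

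2. **The loss is easily overstated.** A reader might cube the printed figure (0.8³ = 51%) and infer that an effective walker would fail about half the time. The documents do not support that. It needs exactly 80% on every row, and Step 1 shows that no single n gives this. With 20 independent values the Table 1 inputs give 68%, a failure chance of about 32%. Nor should 51% be set beside the 24% for 10 patients, since the two rest on different bases.

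3. **24% is a worst case over within-patient correlation.** It holds only if a patient's second powered trial adds no information, or if the Table 1 SD already describes patient averages. This stands, so 24% is one end of a range. The fall from 68% to these values also comes from counting 20 values as 10 patients, not from the all-three rule itself.

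4. **The number analysed is unsettled.** With 24 single differences joint power is about 79%, and with 48 about 99% (both for independent outcomes), so the shortfall might vanish. This also stands, but item 4 as written specifies 10 patients, and under that analysis the shortfall remains.

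**Conclusion.** The point holds as a gap in the power justification. Under the primary analysis as written, the chance of meeting the success rule when every Table 1 difference is real is:

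- about 68% (65–80% over any dependence between outcomes) on the generous reading of 20 independent values;
- 24–63% with one averaged difference from each of 10 patients and independent outcomes, as within-patient correlation goes from 1 to 0.

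These figures assume that the Table 1 differences and SDs are correct. The second range also takes the SD as that of a single difference. Neither the between-outcome nor the within-patient correlation is given, so no one figure can be presented as the trial's power.

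Requiring all three tests to succeed does not inflate type I error. This point is about power only.

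**What to change.** 1. Reconcile the number analysed: 10 patients in the primary analysis section against 24 CP and 24 typically developed subjects in the target.
2. In item 3, state power for the all-three rule at that one number of subjects, with one difference per subject. Say whether the Table 1 SD belongs to a single difference or to a patient average.
3. State the assumed between-outcome and within-patient correlations, and show joint power over a range of each.
4. Amend item 4 so that the analysis matches: the mean of the two powered trials minus the unpowered trial, one value per subject.

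If the 24 CP subjects are analysed, joint power with independent outcomes is about 79%, 91% or 98% at within-patient correlation 1, 0.5 or 0. The sponsor should report that range and not a single figure.

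The cost is rewording of items 3 and 4, with no added enrolment or procedures. The drawback is that the stated power becomes less favourable if only 10 patients are analysed.
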